3.1. Randomization

There is no randomization as this is a single-arm, OL study. Subjects will receive NBI-827104 doses according to their body weight category outlined in [Table 1](#).

3.2. Data Monitoring Committee (DMC)

An independent DMC will periodically review accumulating study data to avoid exposing subjects to excessive risk as a result of the study procedures and treatment. The DMC will consist of at least 3 members, including physicians and a statistician with expertise in the areas of clinical trials, epileptology, and biostatistics. The data review may result in recommendation for early termination of the study or changes to the protocol and informed consent.

The independent DMC will also review the safety and tolerability data from at least [REDACTED] and make a recommendation to the Sponsor for whether the study may continue per the protocol.

A DMC charter describes the responsibilities, timing of meetings, and data review procedures. DMC reports will be provided by an independent statistical center.

3.3. Blinding

There is no blinding for this study.

3.4. Sample Size Considerations

A total sample size of up to approximately 24 subjects is based on the sample size of CSWS2010. [REDACTED]
[REDACTED]

Neurocrine Biosciences, Inc.
Statistical Analysis Plan

Study NBI-827104-CSWS2025
6 September 2024

██████ Efficacy analyses will be based on the full analysis set. All other summaries will be based on the safety analysis set unless otherwise noted.

4.3. General Definitions

4.3.1. Baseline Definition

Baseline ██████

The assessments performed at the Day 1 nominal visit of CSWS2025 will serve as the baseline value for all assessments unless otherwise noted. If a Day 1 nominal visit value is not available, then the last measurement collected prior to the first dose of NBI-827104 in CSWS2025 (hereafter known as the first dose) will serve as baseline. The Day 1 nominal visit data for direct enrollment subjects are collected during the last nominal visit (ie, ██████) of CSWS2010 and transferred to the Day 1 nominal visit of CSWS2025.

██████

██

██

██

██

██

██

██

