2.1.2. NBI-827104 Clinical Experience

NBI-827104 (formerly ACT-709478) is a novel selective and orally available triple T-type calcium channel blocker.

[REDACTED] Considering the role of T-type calcium channels in the pathophysiology of IGE and spike-wave discharges in particular, the nonclinical data, and the unmet medical need, NBI-827104 is being developed for the treatment of EECSWS.

Study NBI-827104-CSWS2010 was a Phase 2, multicenter, randomized, double-blind, placebo-controlled, parallel-group study to evaluate the efficacy, safety, tolerability, and PK of NBI-827104 in pediatric subjects with EECSWS reviewed and approved by an external Diagnosis Confirmation Panel (DCP). [REDACTED]

[REDACTED] For subjects who enroll directly from Study NBI-827104-CSWS2010 to the current Study NBI-827104-CSWS2025, subjects will have completed 12 weeks of either placebo or NBI-827104 study treatment [REDACTED] in Study NBI-827104-CSWS2010. For subjects who do not enroll directly, with a gap between the 2 studies, subjects will have completed 12 or 13 weeks of either

placebo or NBI-827104 study treatment [REDACTED]
[REDACTED] and a [REDACTED] posttreatment safety period in
Study NBI-827104-CSWS2010.

[REDACTED]

[REDACTED]

A complete summary of the available clinical and nonclinical data for NBI-827104 is provided in the Investigator's Brochure.

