3. STUDY DESIGN

This is a Phase 2, multicenter, open-label extension, interventional study to evaluate the long-term safety, tolerability, [REDACTED] of NBI-827104 in pediatric subjects with EECSWS. Eligible subjects may enroll directly following completion of the Week 12 study visit at the end of the maintenance period of Study-NBI-827104-CSWS2010 (known as CSWS2010 hereafter) or after a gap following completion of that study. Subjects who did not participate in CSWS2010 may enroll if [REDACTED]. This study is expected to enroll approximately 24 subjects aged 4 to 12 years (inclusive).

The study will consist of the following periods: a Screening Period [REDACTED], which is applicable only for subjects who do not enroll directly from or did not participate in CSWS2010; a Dose Titration Period [REDACTED]; a Long-Term Treatment Period [REDACTED]; a Dose Taper Period [REDACTED]; a Safety Follow-up Period [REDACTED]. The maximum duration of an individual subject's study participation is up to 242 weeks. For subjects who enroll directly from CSWS2010, the CSWS2025 Day 1 Visit is the same as the CSWS2010 Day 84/Week 12 (End of Maintenance) Visit. Assessments completed as part of the End of Maintenance Visit in CSWS2010 will be transferred to the CSWS2025 Day 1 electronic case report form (eCRF).

A complete Schedule of Assessments is provided in the study protocol.

Screening Period: For subjects who enroll directly from CSWS2010, informed consent/assent may be provided within 28 days prior to Day 1 or on Day 1. Subjects who do not enroll directly or did not participate in CSWS2010 must be provided with informed consent/assent before the start of screening assessments and will be screened to determine eligibility up to 28 days before the start of study treatment dosing on Day 1.

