5. STUDY POPULATION

5.1. Disposition

The summary of subject enrollment and disposition will include:

- The total number of subjects who provided informed consent
- The following categories will be presented. The number of subjects enrolled will serve as the denominator to calculate percentages.
 - Enrolled subjects
 - Direct enrollment by CSWS2010 treatment assignment: subjects who directly rolled over from CSWS2010
 - Non-direct enrollment by CSWS2010 treatment assignment: subjects who enrolled after a gap following completion of CSWS2010
 - De novo enrollment: subjects who did not participate in CSWS2010
 - Completed study drug dosing
 - Discontinued study drug dosing, including reasons
 - Completed study
 - Last Long-Term Treatment Period completed: Schedule A
 - Last Long-Term Treatment Period completed: Schedule B
 - Last Long-Term Treatment Period completed: Schedule C
 - Discontinued study, including reasons
 - Discontinued in Schedule A
 - Discontinued in Schedule B
 - Discontinued in Schedule C

A listing will be provided which includes subject identification (ID), the date of informed consent, the date of enrollment, CSWS2010 treatment assignment, and the dose at Day 1 of CSWS2025.

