5.5. Medical History

Medical history information was entered into the CSWS2025 database by site staff. For subjects that participated in CSWS2010, this included the subject's medical history reported in CSWS2010 as well as any AEs from that study that were ongoing at the time of enrollment into CSWS2025. Medical history will be summarized descriptively for all enrolled subjects. Medical history data will be coded using MedDRA. Data will be summarized with frequencies and percentages of subjects with at least one medical history item, and subject frequencies and percentages according to the system organ class (SOC) and preferred term (PT) levels. The table will be sorted alphabetically by SOC and then, within an SOC, by PT.

Neurocrine Biosciences, Inc.
Statistical Analysis Plan

Study NBI-827104-CSWS2025
6 September 2024

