9.7. Electrocardiogram

The triplicate ECG parameter values recorded at each timepoint for heart rate, PR interval, QRS duration, QT interval, and QTcF (corrected QT interval using Fridericia's formula) interval will be averaged (and rounded to the nearest whole number) for each subject and timepoint for the purpose of statistical summarization. Additionally, for the triplicate investigator overall categorical assessment (ie, Normal, Abnormal not Clinically Significant, or Abnormal Clinically Significant) at each timepoint, the outcome representing the greatest degree of abnormality will be selected for summarization.

Descriptive statistics for the observed values and change from baseline will be presented for each of the ECG parameters by timepoint.

Frequency tables (number and percentage of subjects) will be presented for the overall categorical assessment at each timepoint.

Two additional categorical summaries (frequency tables displaying number and percentage of subjects) will be presented for the QTcF interval. For the first summary, the observed QTcF values at each timepoint will be classified as follows:

- Greater than 450 msec
- Greater than 480 msec
- Greater than 500 msec

For the second categorical summary, the change from baseline to each subsequent timepoint will be classified as follows:

- Increase greater than 30 msec
- Increase greater than 60 msec

The same categorical summaries will be presented in frequency tables for values at any postdose timepoint (including unscheduled assessments) meeting the aforementioned criteria.

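### For direct rollovers from the NBI-827104 arm of CSWS2010, the visible baseline is an on-drug value, so the change-based safety summaries omit any effect already present at Day 1

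*SAP*

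**What the plan says.** SAP 4.3.1 sets one default for every enrollment route: "The assessments performed at the Day 1 nominal visit of CSWS2025 will serve as the baseline value for all assessments unless otherwise noted". If the Day 1 value is missing, "then the last measurement collected prior to the first dose of NBI-827104 in CSWS2025 (hereafter known as the first dose) will serve as baseline". SAP 3 and 4.3.1 explain that, for direct enrollees, the Day 1 data are carried over from the CSWS2010 End of Maintenance visit (Day 84/Week 12). Protocol 2.1.2 says that by then "subjects will have completed 12 weeks of either placebo or NBI-827104 study treatment". Other subjects enroll after a gap that follows the CSWS2010 posttreatment safety period, or are new to the program.

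The following outputs use that baseline:

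- **ECG (SAP 9.7):** change in each parameter. For QTcF increases of more than 30 and more than 60 msec, "the change from baseline to each subsequent timepoint will be classified as follows".
- **Vital signs, weight and BMI (SAP 9.6):** change from baseline, beside observed values.
- **Hematology and chemistry (SAP 9.3):** shift tables from baseline in low/normal/high categories. A value that is high at baseline and still high later is grouped with the non-adverse shifts.

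On adverse events, SAP 5.5 puts into medical history the history reported in CSWS2010 "as well as any AEs from that study that were ongoing at the time of enrollment into CSWS2025". Under SAP 9.2 a condition already present is a TEAE only if it worsens in intensity or frequency after dosing starts in this study.

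Prior treatment is used in SAP 5.1, where disposition has the row "Direct enrollment by CSWS2010 treatment assignment", a matching row for non-direct enrollment, and a listing that shows the assignment. No visible safety section splits by it.

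**The concern.** The primary objective is the long-term safety and tolerability of the drug. A change from baseline describes a drug effect only if the baseline is free of that effect. For direct rollovers from the NBI-827104 arm it is not: the Day 1 ECG, laboratory values, vital signs and weight were measured at the end of 12 weeks of treatment. An effect that appeared in CSWS2010 and persists will show as little or no change. The visible tables then pool these subjects with prior-placebo, gap and de novo subjects, for whom Day 1 is an off-drug value, so one column mixes two kinds of change.

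Adverse events have a parallel gap. An event that began on NBI-827104 in CSWS2010 and continues unchanged appears in this study only as medical history. With about 24 subjects, a few QTcF flags or persistent events that go uncounted could alter the impression the tables give.

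**Working it through.** The plan gives no figure to reproduce: the sample size is taken from CSWS2010, and Protocol 11.1 states that the primary endpoint is not formally tested. The check is a reading of the definitions, followed by an illustration on assumed values.

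**1. Which subjects have an on-drug baseline**

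| Enrollment route | State at Day 1 | Baseline |
|---|---|---|
| Direct, NBI-827104 arm | end of 12 weeks on drug | on-drug |
| Direct, placebo arm | end of 12 weeks on placebo | off-drug |
| Gap after CSWS2010 | after its posttreatment safety period | off-drug |
| De novo | not in CSWS2010 | off-drug |

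Only the first row is affected. The fallback rule does not help that row, because the last value before the first dose in this study is generally also an on-treatment value.

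**2. What is removed.** SAP 4.3.2 defines change as postbaseline minus baseline. Let E be the true effect at a later visit against a drug-free value, E0 the effect already present at Day 1 in the affected group, and f the share of all subjects in that group.

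- Affected subject: reported change = E − E0
- Any other subject: reported change = E
- Pooled mean change = (1 − f)·E + f·(E − E0) = E − f·E0

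The shortfall is f·E0. An effect that first appears after Day 1, for example at a higher dose level, stays in E and is still seen.

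**3. Mean QTcF change** (E, E0 and f are all assumptions)

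| E0, E (msec) | f = 0 | f = 0.25 | f = 0.50 | f = 0.75 |
|---|---|---|---|---|
| 10, 10 | 10 | 7.5 | 5 | 2.5 |
| 20, 30 | 30 | 25 | 20 | 15 |

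**4. QTcF increase above 30 msec.** Assume a normal distribution, an SD of change of 15 msec, and E = E0 = 20 msec.

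- Off-drug baseline: 1 − Φ((30 − 20)/15) = 25.2%
- On-drug baseline: 1 − Φ((30 − 0)/15) = 2.3%
- Pooled at f = 0.25, 0.50, 0.75: 19.5%, 13.8%, 8.0%
- Expected number flagged out of 24: 6.1 at f = 0, then 4.7, 3.3 and 1.9

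For a single subject who is 20 msec above the drug-free value at rollover and later 35 msec above it, the recorded change is 35 − 20 = 15 msec, below the 30 msec flag.

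**5. Laboratory shifts.** A value that rose from normal to high on drug in CSWS2010 and remains high is recorded as high to high, and so as non-adverse. Against a value from before NBI-827104 it would be normal to high.

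**6. What does not depend on baseline.** This covers observed ECG and vital-sign values, the QTcF categories above 450, 480 and 500 msec, the by-visit laboratory categories, and the potentially clinically significant laboratory results.

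**The case against.** The strongest reply is that part of SAP 4.3.1 is blacked out directly after the Day 1 definition. The default applies only where nothing else is noted, and Protocol 11.5 allows the SAP to add baseline definitions. Most of the SAP between 3.4 and 4.3 is also not visible, and general presentation rules could be there. This stands: nobody can say from these documents that the plan has no second baseline or no split by prior treatment. What can be said is that the visible text of SAP 9.3, 9.6 and 9.7 refers to baseline without naming another one.

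Second, Day 1 is a coherent reference for change during the extension. Replacing it for one subgroup would mix baselines about 12 weeks apart in growing children, which matters for weight and vital signs. This also stands, and is why Day 1 should remain the main display.

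Third, several stronger readings are tempting but not supported:

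- **That drug effects as a whole are subtracted.** Only E0 cancels. Protocol 4.3 says mean exposure in CSWS2010 was below the target range, and that this is why DL 4 and possibly DL 5 were added; effects added there remain visible.
- **That laboratory changes are subtracted.** SAP 9.3 excludes numeric change for hematology and chemistry. Only the shift tables depend on baseline.
- **That early changes reflect a step down to DL 1.** All subjects do start at DL 1, but the dose at exit from CSWS2010 is not visible.
- **That every table leans toward apparent safety.** Early changes could go either way, and the displays in step 6 do not depend on baseline at all.
- **That the primary endpoint is biased by the baseline.** Serious TEAEs are not a change measure. An event ongoing from CSWS2010 counts if it worsens, and is otherwise coded and tabulated as medical history. Nothing shows that any such event was caused by the drug.

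**Conclusion.** The concern holds in limited form. On the visible text, direct rollovers from the NBI-827104 arm are measured against an on-drug baseline. Their ECG, vital-sign and weight changes, QTcF increase categories and laboratory shift categories therefore omit any effect already present at Day 1.

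The size cannot be estimated from the documents. The number of such subjects, the CSWS2010 allocation and E0 are not given, and with f = 0 there is no bias. Nor does a 1:1 allocation, if assumed, cap f at one half, because f depends on who enrolled and by which route. The millisecond and percentage figures above are illustrations only.

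A supplementary display is still worth adding. The objective is long-term safety, and a persistent effect in these subjects would be hard to see in the change tables. The conclusion is conditional on the redacted text not already providing the display.

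**What to change.** Keep CSWS2025 Day 1 as the main baseline. The sponsor should first confirm whether the redacted part of SAP 4.3.1 defines a baseline from before NBI-827104, and whether SAP 9.3, 9.6 and 9.7 use it. If not:

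1. Add a supplementary display of ECG and QTcF change, the >30 and >60 msec categories, vital-sign change and laboratory shifts. For direct rollovers from the NBI-827104 arm, use the last value before their first NBI-827104 dose in CSWS2010; for all others keep Day 1.
2. Show the change-based safety tables for prior-NBI-827104 direct rollovers and for all other subjects, beside the total.
3. List or count the AEs that began on NBI-827104 in CSWS2010 and were still ongoing at Day 1.

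The cost is SAP wording, merging CSWS2010 assessment data, and extra columns with small cells at about 24 subjects. CSWS2010 treatment assignment and ongoing AEs are already used in SAP 5.1 and 5.5, so some linkage exists. Study conduct does not change.

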4.3.2. Derived and Transformed Data

Change from baseline is calculated as the postbaseline value minus the baseline value unless otherwise noted. Percent change from baseline is calculated as change from baseline/baseline value $\times 100$ unless otherwise noted. If either the baseline or postbaseline value is missing, the change from baseline and/or percent change from baseline will also be missing. The percent change from baseline will also be missing if the baseline value is equal to zero.

4.3.3. Study Day

Study day is calculated relative to the date of Day 1, where Day 1 is defined as the date the subject received their first dose in CSWS2025. If the date of interest occurs on or after Day 1, then the study day will be calculated as: date of interest – date of Day 1 + 1. If the date of interest occurs prior to Day 1, then the study day will be calculated as: date of interest – date of Day 1.

4.3.4. Early Termination Data

Early termination (ET) data collected at postbaseline unscheduled visits will be mapped to the next subsequent visit where the applicable assessment would have been performed for the purpose of statistical summarization. ET data collected at a scheduled visit per the protocol schedule of assessments will be mapped to that scheduled visit for applicable data summaries.

Neurocrine Biosciences, Inc.
Statistical Analysis Plan

Study NBI-827104-CSWS2025
6 September 2024

4.3.5. Handling of Missing Data

4.3.5.1. Start Dates for Adverse Events (AEs)

Missing and incomplete dates for AEs will be imputed for the purpose of estimating the time of the event in relationship to study treatment.

The imputation rules for AE start dates are as follows:

- If the date is completely missing, the date will be imputed as the date of the first dose;
- If only the day is missing, the date will be imputed as the date of the first dose if the month and year of the AE start date match the month and year of the first dose; otherwise, the missing day will be imputed as the first day of the month;
- If both the day and month are missing, the date will be imputed as the date of the first dose if the AE start date is in the same year as the first dose; otherwise, the missing day and month will be imputed as 01 January;
- If any of the above imputations result in a start date that is later than an existing (not imputed) end date for the event, the start date will be imputed as the end date.

There will be no imputation for AE stop dates.

4.3.5.2. Start and Stop Dates for Medications

Missing and incomplete dates for medications will be imputed for the purpose of estimating the time of medication usage relative to study treatment. Medications from the antiseizure medication history eCRF page are assumed to be prior medications and imputation of dates will not be performed.

The imputation rules for medication start dates are as follows:

- If the date is completely missing, the date will be imputed as the date of the subject's first dose;
- If only the day is missing, the date will be imputed as the date of the first dose if the medication start date is in the same month and year as the first dose; otherwise, the missing day will be imputed as the first day of the month;
- If both the day and month are missing, the date will be imputed as the date of the first dose if the medication start date is in the same year as the first dose; otherwise, the missing day and month will be imputed as 01 January;
- If any of the above imputations result in a start date which is later than an existing (not imputed) medication stop date, the start date will be imputed as the stop date.

The imputation rules for medication stop dates are as follows:

- If the date is completely missing, the date will be imputed as the date of the subject's last dose;
- If only the day is missing, the date will be imputed as the date of the last dose if the medication stop date is in the same month and year as the last dose; otherwise, the missing day will be imputed as the last day of the month;

Neurocrine Biosciences, Inc.
Statistical Analysis Plan

Study NBI-827104-CSWS2025
6 September 2024

- If both the day and month are missing, the date will be imputed as the date of the last dose if the medication stop date is in the same year as the last dose; otherwise, the missing day and month will be imputed as 31 December;
- If any of the above imputations result in a stop date which is earlier than an existing (not imputed) medication start date, the stop date will be imputed as the start date.

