9.9. Prior and Concomitant Medications

Prior and concomitant medications will be summarized by WHO Drug Anatomical Therapeutic Chemical Classification (ATC) Level 3 category (or Level 2 if there is not an applicable Level 3 category) and preferred names. Medications from the antiseizure medication history eCRF page are assumed to be prior medications and imputation of dates will not be performed. Missing start and stop dates will be handled according to Section 4.3.5.2.

Medications will be summarized in frequency tables. The frequency tables will include the number and percentage of unique subjects reporting the medication one or more times. For medications, the table will be sorted alphabetically by ATC class and then, within an ATC class, by preferred names. Prior and concomitant medications are defined as mutually exclusive categories according to the first dose as follows:

■	[REDACTED]
	[REDACTED]
	[REDACTED]
■	[REDACTED]
■	[REDACTED]
	[REDACTED]
	[REDACTED]
■	[REDACTED]
	[REDACTED]
■	[REDACTED]
	[REDACTED]
	[REDACTED]

Neurocrine Biosciences, Inc.
Statistical Analysis Plan

Study NBI-827104-CSWS2025
6 September 2024

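### The medication date rules check order only against a recorded date, so some pairs of incomplete dates give a drug that ended before Day 1 a start on the first-dose date, after its own imputed stop

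*SAP*

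**What the plan says.** SAP 4.3.5.2 handles medication dates in two separate lists.

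**Start dates.**
- Wholly missing: "If the date is completely missing, the date will be imputed as the date of the subject's first dose".
- Day missing: the first-dose date applies "if the medication start date is in the same month and year as the first dose; otherwise, the missing day will be imputed as the" (the fallback is day 1 of the recorded month).
- Day and month missing: the first-dose date applies "if the medication start date is in the same year as the first dose; otherwise, the missing day and month will be imputed as 01" (the fallback is 1 January of the recorded year).
- Order check: "If any of the above imputations result in a start date which is later than an existing (not imputed) medication stop date, the start" (in that event the start is moved back to the recorded stop).

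**Stop dates.**
- Wholly missing: "If the date is completely missing, the date will be imputed as the date of the subject's last dose".
- Day missing: the last-dose date applies "if the medication stop date is in the same month and year as the last dose; otherwise, the missing day will be imputed as the" (the fallback is the final day of the recorded month).
- Day and month missing: the last-dose date if the year is the last-dose year, otherwise 31 December.
- Order check: "If any of the above imputations result in a stop date which is earlier than an existing (not imputed) medication start date, the stop" (in that event the stop is moved forward to the recorded start).

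Entries from the antiseizure medication history page are treated as prior and their dates are not imputed. No visible rule covers the case in which both dates are imputed.

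The imputed dates are used in SAP 9.9: "Prior and concomitant medications are defined as mutually exclusive categories according to the first dose". The definitions that follow are redacted in the public copy.

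**The concern.** The two order checks show that the authors wanted every medication interval to run forwards. Each check compares an imputed date only with a recorded one, so a record with two imputed dates escapes both.

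Some of those records still carry enough information to show that use ended before Day 1, because the stop month or year is known. Moving the start to the first-dose date overrides that information and produces an interval that cannot exist. The section says imputation is there to place medication use in time relative to study treatment, and in these records it places the start on the wrong side of the first dose.

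At stake are the derived dates and, depending on the redacted definitions, the split between prior and concomitant medications. If nothing is added, each programmer must decide how to treat a start that follows its own stop.

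**Working it through.** **Inputs.** The imputation rules and order checks are those of SAP 4.3.5.2. The calendar dates below are assumptions chosen to exercise the rules. The documents give no subject-level dates, and the plan states no figure to reproduce.

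**Worked example.** First dose 10 Mar 2022.

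1. Start missing, or recorded only as 2022: imputed to 10 Mar 2022.
2. Stop recorded as Jan 2022, which is not the last-dose month: imputed to 31 Jan 2022.
3. Start check: needs a stop that was not imputed. The stop was imputed, so the check does not apply.
4. Stop check: needs a start that was not imputed. The start was imputed, so the check does not apply.
5. Result: start 10 Mar 2022, stop 31 Jan 2022. The gap is 28 days of February + 10 days of March = 38 days, in the wrong direction.

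Had the stop been recorded in full, say 20 Jan 2022, the start check would have moved the start to 20 Jan 2022.

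**Which patterns can invert.** Take a drug that truly ended before Day 1 and cross three kinds of incomplete start with three kinds of incomplete stop:

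| Start known to | Stop known to | Can start fall after stop? |
|---|---|---|
| nothing | month and year | Yes, if the stop month precedes the first-dose month |
| nothing | year | Yes, if the stop year precedes the first-dose year |
| nothing | nothing | No: first dose to last dose |
| year | month and year | Yes, if the start year is the first-dose year and the stop month precedes the first-dose month |
| year | year | No |
| year | nothing | No |
| month and year | month and year | No |
| month and year | year | No |
| month and year | nothing | No |

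So 3 of the 9 patterns can invert.

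**Check on a second set of dates.** With first dose 15 Jun 2022 and last dose either 15 Jun 2024 or 15 Sep 2022, the rules applied literally give:

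| Recorded start | Recorded stop | Imputed interval | Inverted? |
|---|---|---|---|
| missing | May 2022 | 15 Jun 2022 to 31 May 2022 | Yes |
| 2022 | May 2022 | 15 Jun 2022 to 31 May 2022 | Yes |
| missing | 2021 | 15 Jun 2022 to 31 Dec 2021 | Yes |
| Mar 2022 | May 2022 | 01 Mar 2022 to 31 May 2022 | No |
| 2021 | 2021 | 01 Jan 2021 to 31 Dec 2021 | No |
| 2021 | May 2022 | 01 Jan 2021 to 31 May 2022 | No |
| 2022 | 10 May 2022 (complete) | 10 May 2022 to 10 May 2022 | No, the check works |

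Running all nine patterns over a grid of true start and stop dates from 1 Jan 2021 to 14 Jun 2022 gave inversions in the same three patterns and none in the other six, under both last-dose dates.

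**Can such a record be collected?** Protocol 7.1 asks for all medications taken in the 30 days before screening, or before Day 1 for direct enrollers. SAP Section 3 puts screening up to 28 days before Day 1.

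- Screened subject: first dose 10 Mar 2022 − 28 days = screening 10 Feb 2022; − 30 days = 11 Jan 2022. A stop in Jan 2022 can be in scope.
- Direct enroller: 10 Mar 2022 − 30 days = 8 Feb 2022. A stop in Jan 2022 is outside the window, but Feb 2022 can be inside it. With the start missing, that record becomes start 10 Mar 2022, stop 28 Feb 2022, inverted by 10 days.

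**Effect of the fix.** Checking the imputed start against an imputed stop as well gave no inverted record in any of the nine patterns. In the worked example both dates become 31 Jan 2022, before the first dose.

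**The case against.** Several readings stronger than the defect are tempting. The case against them is good.

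- **Any pre-Day 1 drug with two incomplete dates is affected.** It is not. Six of the nine patterns never invert, and many of those pairs correctly get a start before Day 1. In some others, such as both dates known only to the first-dose year, the start goes to the first dose but the stop is later still. That may misplace a drug, but it contradicts nothing recorded.
- **The drug will be tabulated as concomitant, or fit neither category.** A reader might infer this, and a shift of 1/24 = 4.2 percentage points in a table row, from SAP 9.9. The definitions are redacted. If prior means stopped before first dose, the worked example is classed correctly whatever its start. The shift would also need the subject to have no other qualifying record in that row, because the tables count unique subjects.
- **False protocol deviations will follow.** SAP 5.3 tracks deviations under a separate plan with study-team review, and nothing visible feeds imputed dates into it. The barred period for steroids and IVIG before screening is redacted, so a recorded pre-study use could already be a genuine breach.
- **Drugs stopped before screening are the likeliest to have two incomplete dates.** No passage supports a statement about frequency.
- **Data cleaning will catch it.** Protocol 12.2 provides logic checks, manual review and site queries, which should reduce incomplete dates. This stands in part. A missing start with a stop of Jan 2022 is incomplete but not contradictory as recorded; the contradiction arises in the derivation. A query that cannot be answered leaves it in place.

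None of this touches the mechanism. Both checks require a recorded counterpart, and no visible rule takes over when there is none.

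**Conclusion.** The point holds as a minor drafting gap. For medications outside the antiseizure medication history page, a start that is wholly missing (with a partial stop in a month before the first-dose month or a year before the first-dose year), or a start known only to the first-dose year (with a stop month before the first-dose month), is placed on the first-dose date and after the drug's own imputed stop. In the example the inversion is 38 days. It is certain for any record meeting those conditions, provided the rules are programmed as written.

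The number of such records is not known. Misclassification as concomitant is possible but cannot be established from the public text. The effect is confined to descriptive medication data. The primary endpoint, the occurrence of serious treatment-emergent adverse events, does not use these dates.

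**What to change.** In SAP 4.3.5.2, state that the stop date is imputed first, and replace the start-date check with:

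> If the imputed start date is later than the recorded or imputed stop date, the start date is set to the stop date.

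The existing stop-date check, against a recorded start, can stay as it is. Records whose recorded parts do not place use before Day 1 are unaffected.

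Separately, the sponsor should confirm that the redacted SAP 9.9 definitions class as prior any medication whose partial stop lies wholly before the first dose. If they already do, nothing needs adding there.

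The cost is one sentence in the SAP and one line of code before database lock. No recorded information is lost.
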